6.3.19 Storage of M. tuberculosis bacterial isolates

Any *M. tuberculosis* bacterial isolates from screening, as well as isolates cultured from specimens obtained after screening will be stored. Isolates should be labeled with study identification number and collection date, and not with participant name.

6.3.20 Storage of biospecimens

Blood and CSF specimens will be stored from consenting participants. Specimens collected for storage will be labeled with study identification number and collection date, and will not be labeled with participant name. Specimens will be stored at the site and shipped in batches to the US-based team for testing. Additionally, samples should be collected a) if failure or relapse is suspected and the participant is evaluated at an unscheduled or sick visit or b) if a participant voluntarily withdraws from the study. Participant consent for collection and storage of specimens will be part of the study consent

form which will be administered during the entry visit, with an independent signature line.

7.0 ADVERSE EVENTS AND STUDY MONITORING

7.1 Definition of Adverse Events

An adverse event (AE) is any unfavorable and unintended sign (including an abnormal laboratory finding), symptom, or diagnosis that occurs in a study participant during the conduct of the study REGARDLESS of the attribution (i.e., relationship of event to medical treatment/study product/device or procedure/intervention). This includes any occurrence that is new in onset or aggravated in severity or frequency from the baseline condition.

7.2 Adverse Event Collection Requirements for this Study

All AEs must be recorded on the CRFs if any of the following criteria have been met.

- All Grade 3 to 5 AEs
- All AEs that led to a change in study treatment/intervention regardless of grade
- All AEs meeting serious adverse event definition or expedited adverse event reporting requirement

All AEs that are reported must have their severity graded. AEs will be graded according to the Division of AIDS Table for Grading the Severity of Adult and Pediatric Adverse Events (DAIDS AE Grading Table), Corrected Version 2.1, July 2017, which can be found on the DAIDS RSC website at https://rsc.niaid.nih.gov/clinical-research-sites/daids-adverse-event-grading-tables

Serious Adverse Events (SAEs)

A SAE is defined as any untoward medical occurrence that:

- Results in death
- Is life-threatening
- Requires inpatient hospitalization or prolongation of existing hospitalization
- Results in persistent or significant disability/incapacity
- Is a congenital anomaly/birth defect
- Is an important medical event that may not be immediately life-threatening or result in death or hospitalization but may jeopardize the patient or may require intervention to prevent one of the other outcomes listed in the definition above.

All pre-existing conditions present at study entry **must be clearly documented on the CRF at entry.** If the frequency, intensity, or the character of the condition worsens to Grade 3 to 5 level during the reporting period, the event should be defined as an AE.

7.3. Reporting Requirements for this Study

- Requirements, definitions and methods for expedited reporting of AEs are outlined in Version 2.0 of the DAIDS EAE Manual, which is available on the RSC website at https://rsc.niaid.nih.gov/clinical-research-sites/manual-expedited-reporting-adverse-events-daids.
- The SAE Reporting Category, as defined in Version 2.0 of the DAIDS EAE Manual, will be used for this study from the time of enrollment through week 8 for all participants. For the remainder of the trial, only SAEs which are judged by the site as having a reasonable possibility of being related to study drug (SARs) should be reported.
- The study agents for which expedited reporting is required are: rifampicin and linezolid
- The expedited AE reporting period for this study is the entire study duration of 24 weeks for an individual participant (from study enrollment until study completion or discontinuation of the participant from study participation for any reason).

7.4 Expected disease-related events

This study population, with TB and advanced HIV, are both critically ill and profoundly immunosuppressed will have a complicated clinical course. Opportunistic and nosocomial infections are expected. Disease-related events will be frequent and include:

- Death due to TBM (~40% enrolled participants). Will always be reported as an SAE.
- Disability due to TBM. Will not be reported as an AE.
- TBM-IRIS events and symptoms. Will not be reported as an AE.
- Neurological complications of TBM, including tuberculoma, infarct, seizures, headache due to raised ICP. **Will not be reported as an AE.**
- Other opportunistic infections. Will not be reported as an AE.
- Nosocomial infections, including hospital acquired pneumonias or aspiration pneumonias. Will not be reported as an AE.

Expected disease-related events do not require reporting unless the severity of the event was considered to be unexpected.

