2.4 SECONDARY ENDPOINTS

1. Proportion of participants with Grade 3 or higher AEs at 4 weeks

2. Proportion of participants who complete LZD treatment

3. Exposure-response (PK-PD) relationship, with LZD as predictor and Grade 3 or higher AE as outcome variable

4. Modified Rankin Scale (death, severe disability, moderately severe, moderate disability, slight disability, no significant disability, no symptoms) at 12 and 24 weeks

5. Montreal Cognitive Assessment (MoCA) or neurocognitive battery performance at 12 and 24 weeks

6. Exposure-response (PK-PD) relationship, with linezolid as predictor and Modified Rankin Scale as outcome variable

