7.6 Recording of AEs

The objective of the AE endpoint is to assess linezolid drug toxicity when administered with high and standard dose rifampicin among this critically ill population with high mortality. AEs grade 3-5 will be recorded via the AE recording CRF. The clinical course of each event should be followed until resolution, stabilization, or until it has been determined that the study treatment is not the cause. All unresolved AEs at study termination should be followed until the events are resolved, otherwise explained.

Asymptomatic laboratory abnormalities are not reportable AEs. However, abnormal laboratory results constitute an AE if the abnormality:

- is associated with a serious adverse event (e.g. death, hospitalization)
- is associated with clinical signs or symptoms
- leads to additional treatment or to further diagnostic tests, (other than repeat lab check), or
- is considered by the investigator to be of clinical significance

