8.1.4 Neurotoxicity

Mild to moderate headache is an expected adverse reaction linezolid, whereas peripheral neuropathy and optic neuropathy are expected to be relatively uncommon over a 4-week treatment period. Study treatment will be stopped for any Grade 3 or higher neurologic adverse events, including neuropathy or visual changes. If participants develop signs/symptoms of optic neuropathy, we will endeavor to have them evaluated by an ophthalmologist in Masaka if safe and logistically feasible. If a participant develops Grade 3 or higher symptoms, linezolid will be discontinued for up to 14 days until symptoms have resolved to Grade ≤ 2 , at which point linezolid 1200 mg can be reintroduced.

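### Sections 7.2 and 7.6 require every Grade 3-5 AE to be recorded, section 7.4 exempts infections and TBM complications from AE reporting, and no section says which rule defines the Grade 3+ AE endpoints

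*Combined protocol and SAP*

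**What the plan says.** All references are to the combined protocol and SAP.

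- **Endpoint.** Section 2.4 lists as secondary endpoint 1 "Proportion of participants with Grade 3 or higher AEs at 4 weeks". Secondary endpoint 3 is an exposure-response relationship with Grade 3 or higher AE as its outcome. Neither excludes any type of event.
- **Definition.** Section 7.1 defines an AE "REGARDLESS of the attribution".
- **Recording.** Section 7.2 requires on the CRF "All Grade 3 to 5 AEs", as well as "All AEs that led to a change in study treatment/intervention regardless of grade" and AEs that meet the serious definition. Section 7.6 repeats that "AEs grade 3-5 will be recorded via the AE recording CRF".
- **Exemption.** Section 7.4 takes five groups out of AE reporting: disability due to TBM, TBM-IRIS, neurological complications of TBM, opportunistic infections ("Other opportunistic infections. Will not be reported as an AE") and nosocomial infections ("Nosocomial infections, including hospital acquired pneumonias or aspiration pneumonias. Will not be reported as an AE"). The infection items carry no limit by grade or causality. Deaths due to TBM are always reported as SAEs. Exempt events become reportable only if their severity was considered unexpected.
- **Blinding.** Section 4.0 describes an open-label trial that will try to keep AE assessors blinded.

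**The concern.** Two members of staff could each follow the protocol and produce different AE data. One, relying on 7.2, completes an AE form for a Grade 3 hospital-acquired pneumonia. The other, relying on 7.4, does not. Both endpoints that use Grade 3+ AEs depend on which of them is followed.

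The exempt groups are not neutral to treatment. Linezolid is an antibacterial, and section 1.0 names myelosuppression among its toxicities, so infections could plausibly fall or rise with it. The link from myelosuppression to infection is an inference, not something the protocol states. Section 1.0 also cites retrospective data linking linezolid with better neurologic outcomes, and neurological complications of TBM are exempt. For those complications, someone must judge that the event is due to TBM and that its severity was expected. No criterion is given for either judgement, and blinding of the assessor is not assured.

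**Working it through.** **1. Which rule governs?** Set side by side:

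| Event | 7.1, 7.2, 7.6 | 7.4 |
|---|---|---|
| Grade 3+ nosocomial or opportunistic infection | Record | Not an AE report, unless severity unexpected |
| Same infection, prolonging hospitalization | Record; meets the SAE definition | Same exemption |
| Grade 3+ seizure or infarct attributed to TBM | Record | Same exemption |
| Grade 3+ neuropathy or visual change | Record | Not listed |
| Grade 3+ myelosuppression | Record | Not listed |
| Death | Record | Always an SAE |

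The first three rows conflict and the last three do not. No section sets an order of precedence.

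**2. Could 7.4 concern expedited reporting only?** Section 7.5.1 already exempts serious events related only to disease progression from 24-hour reporting. Section 7.5.4 already exempts expected disease-related events from SUSAR reporting. If 7.4 meant no more than that, it would largely repeat them, and its wording refers to AEs as such. The narrow reading is possible but not secure.

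**3. The plan's own AE figure.** Section 10.1 states at least 80% power for myelosuppression of 40% versus 10%, with 30 per arm and a 0.05 level (two-sided assumed here).

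- Normal approximation: z = [0.30·√30 − 1.96·√(2·0.25·0.75)] / √(0.4·0.6 + 0.1·0.9) = (1.643 − 1.200) / 0.574 = 0.77, giving 78.0% power.
- Exact enumeration with the uncorrected chi-square test: 79.6%.
- Size for 80% power by the same approximation: 32 per arm.

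The figure reproduces to rounding with the uncorrected test. Myelosuppression is not on the 7.4 list, so this comparison does not change. No power is stated for the all-type Grade 3+ endpoint, and section 10.2 describes no analysis of it.

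**4. Illustration of direction.** The documents give no rates for the exempt events, so all exempt-event rates below are assumed. Take myelosuppression at m = 40% with linezolid and 10% without as the only other Grade 3+ AE, and let exempt Grade 3+ events occur independently with probability e. Then

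P(any Grade 3+) = 1 − (1 − m)(1 − e).

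For e = 20% in both arms: 1 − 0.6·0.8 = 52% and 1 − 0.9·0.8 = 28%. Under 7.4 the recorded proportions are 40% and 10% in every row, a difference of 30 points.

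| e, linezolid / none | All Grade 3+ events | Difference (points) | Power, 30 per arm |
|---|---|---|---|
| 20% / 20% | 52% / 28% | 24 | 47.4% |
| 40% / 40% | 64% / 46% | 18 | 28.5% |
| 20% / 40% | 52% / 46% | 6 | 6.7% |
| 10% / 30% | 46% / 37% | 9 | 10.4% |
| 40% / 20% | 64% / 28% | 36 | 81.5% |
| 30% / 10% | 58% / 19% | 39 | 89.4% |

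The same recorded difference of 30 points can overstate or understate the difference in all Grade 3+ events.

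**The case against.** The best defence is that 7.4 speaks of reporting while 7.2 and 7.6 speak of recording, and that excluding background disease events is reasonable when section 7.6 sets the aim as assessing linezolid toxicity in a critically ill population. The illustration supports part of this: exempt events equally common in both arms shrink a 30-point difference to 24 or 18. That argument stands as a reason to show results without such events. It is not a reason to leave their recording undecided.

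Several stronger readings are tempting, and the documents do not support them.

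- *These events are barred from the record.* Section 7.4 keeps an exception for unexpected severity, and 7.2 still requires events that are serious or change treatment. The text is contradictory; it is not a clean bar.
- *The information is lost.* Section 6.3.2 appears to have Grade 2 or higher signs and symptoms recorded, 6.3.3 all concomitant medications, 6.3.13 all laboratory values, and 6.3.15 daily inpatient GCS and focal signs. What may be missing is a graded diagnosis, such as pneumonia or IRIS, on an AE form.
- *All neurological toxicity is exempt.* Only complications of TBM are. Neuropathy and visual change are not listed.
- *Linezolid headache is hidden.* Section 8.1.4 says "Mild to moderate headache is an expected adverse reaction linezolid"; headache of that severity would not count as Grade 3+, and 7.4 exempts only headache due to raised ICP.
- *The safety comparison fails.* The AE comparison that is powered and tested is myelosuppression.
- *Unblinded staff decide what is dropped.* Blinding is intended though not assured, and the infection items are exempt by type, so judgement enters mainly through attribution to TBM and unexpected severity.

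**Conclusion.** The inconsistency is real and worth correcting, but its reach is limited. It leaves secondary endpoint 1, and endpoint 3 as defined in section 2.4, without a settled definition. If 7.4 is followed, the Grade 3+ proportion is understated by the share of participants whose only Grade 3+ events are exempt, and the between-arm difference may be biased in either direction. The 6 to 39 points set against a recorded 30 show direction only; they rest on assumed rates, on independence, and on myelosuppression being the only other Grade 3+ AE.

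The myelosuppression comparison, deaths, the Modified Rankin Scale, laboratory values and recorded signs and symptoms are not affected.

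**What to change.** Reconcile sections 7.2, 7.4 and 7.6:

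1. State that every Grade 3-5 event goes on the AE CRF, with a flag for expected disease-related events.
2. Limit 7.4 to exemption from expedited and SUSAR reporting, with deaths still reported as SAEs.
3. In section 10.2, report secondary endpoint 1 with and without flagged events, and say which version serves as the outcome for endpoint 3.

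This takes a wording change, one tick-box on the CRF and one additional tabulation. The real cost is more AE forms in a population where such events are expected to be frequent. Reporting endpoint 1 both ways also answers the dilution argument, because the toxicity-focused result remains visible.

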7.5 Evaluation of events

The PI and site PI will monitor the conduct and safety of the study via regular summaries of accrual rates, deaths, SAEs, AEs, and study discontinuation, as appropriate.

The PI and/or site PI will evaluate all SAEs received for seriousness, expectedness and causality. Investigator reports of suspected unexpected serious adverse reactions (SUSAR) will be reviewed and those that are SUSARs identified and reported to the regulatory authorities.

7.5.1 Assessment of Seriousness

When an AE occurs the investigator must first assess whether the AE is serious or not using the definition in Section 7.2. If the event is serious and not only related to disease progression it must be reported within 24 hours of the investigator becoming aware of the event. The regulatory authorities

must then be notified within 7 days.

7.5.2 Assessment of Severity

The Division of AIDS Table for Grading the Severity of Adult and Pediatric Adverse Events (DAIDS AE Grading Table), Corrected Version 2.1, July 2017, must be used to determine severity of events and is available on the DAIDS RSC website at https://rsc.niaid.nih.gov/clinical-research-sites/daids-adverse-event-grading-tables.

7.5.3 Assessment of Causality

The investigator must determine causality in relation to rifampicin and linezolid, based on temporal relationship and clinical judgment. The degree of certainty about causality will be assigned using the definitions in Table 6. If causality is assessed as unrelated or unlikely to be related it is classed as an SAE. If the event is possibly, probably or definitely related, then the event is classed a serious adverse reaction (SAR).

7.5.4 Assessment of Expectedness

If there is at least a possible involvement of the trial treatment, the investigator must assess the expectedness of the event. An unexpected adverse reaction (UAR) is one not previously reported in summary of product characteristics or more severe than previously reported. If an SAR is assessed as unexpected, it becomes a SUSAR, Expected disease-related events will not be reportable as SUSARs.

Side-effects of rifampicin and linezolid should be checked in the latest version of the summary of product characteristics at: http://www.medicines.org.uk/emc

Relationship	Description	SAE Type
Unrelated	The AE is completely independent of study drug administration, and/or evidence exists that the event is definitely related to another aetiology. There must be an alternative, definitive aetiology documented.	Unrelated SAE
Unlikely	A clinical event, including an abnormal laboratory test result, whose temporal relationship to drug administration makes a causal relationship improbable (e.g., the event did not occur within a reasonable time after administration of the trial medication) and in which other drugs or chemicals or underlying disease provides plausible explanations (e.g., the subject's clinical condition, other concomitant treatments).	Unrelated SAE
Possible	There is some evidence to suggest a causal relationship (e.g., the event occurred within a reasonable time after administration of the trial medication). However, the influence of other factors may have contributed to the event (e.g., the subject's clinical condition, other concomitant events). Although an adverse drug event may rate only as "possibly related" soon after discovery, it can be flagged as requiring more information and later be upgraded to "probably related" or "definitely related", as appropriate – for example should a re-challenge occur with the same effect.	SAR
Probable	There is evidence to suggest a causal relationship, and the influence of other factors is unlikely. The clinical event, including an abnormal laboratory test result, occurs within a reasonable time sequence to administration of the drug, is unlikely to be attributed to concurrent disease or other drugs or chemicals, and follows a clinically reasonable response on withdrawal (de-challenge).	SAR
Definite	There is clear evidence to suggest a causal relationship and other possible contributing factors can be ruled out. The clinical event, including an abnormal laboratory test result, occurs in a plausible time relationship to drug administration and cannot be explained by concurrent disease or other drugs or chemicals. The response to withdrawal of the drug (de-challenge) should be clinically plausible. The event must be pharmacologically definitive, with use of a satisfactory re-challenge procedure, if necessary or appropriate	SAR

Table 6: Assigning type of SAE through causality

7.6 Recording of AEs

The objective of the AE endpoint is to assess linezolid drug toxicity when administered with high and standard dose rifampicin among this critically ill population with high mortality. AEs grade 3-5 will be recorded via the AE recording CRF. The clinical course of each event should be followed until resolution, stabilization, or until it has been determined that the study treatment is not the cause. All unresolved AEs at study termination should be followed until the events are resolved, otherwise explained.

Asymptomatic laboratory abnormalities are not reportable AEs. However, abnormal laboratory results constitute an AE if the abnormality:

- is associated with a serious adverse event (e.g. death, hospitalization)
- is associated with clinical signs or symptoms
- leads to additional treatment or to further diagnostic tests, (other than repeat lab check), or
- is considered by the investigator to be of clinical significance

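### Section 7.6 can keep clinically silent Grade 3 or higher cytopenias out of the Grade 3+ AE endpoints, contradicting the AE definition in 7.1, and 10.2 names no data source for myelosuppression

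*Combined protocol and SAP*

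**What the plan says.** Section 7.1 defines an AE as "any unfavorable and unintended sign (including an abnormal laboratory finding"), a symptom or a diagnosis, whatever the cause. It adds: "This includes any occurrence that is new in onset or aggravated in severity or frequency from the baseline condition". Nothing there requires a laboratory finding to be symptomatic.

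Section 7.2 lists which AEs go on the case report form, the first entry being "All Grade 3 to 5 AEs". It adopts the DAIDS table for grading.

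Section 7.6, on recording AEs, opens with the purpose of the data: "The objective of the AE endpoint is to assess linezolid drug toxicity when administered with high and standard dose rifampicin". It continues "AEs grade 3-5 will be recorded via the AE recording CRF", and then "Asymptomatic laboratory abnormalities are not reportable AEs". An abnormal result becomes an AE if it is linked to a serious event, if it comes with signs or symptoms, if it "leads to additional treatment or to further diagnostic tests, (other than repeat lab check), or" if it "is considered by the investigator to be of clinical significance".

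Section 2.4 has two endpoints built on Grade 3 or higher AEs: the proportion of participants affected at 4 weeks, and an exposure-response relationship with linezolid as predictor. Section 10.2 makes Grade 3 or higher myelosuppression the main outcome of the linezolid AE evaluation, and adds linezolid discontinuation or dose reduction attributed to an AE as a secondary outcome. It gives no data source for either. Section 6.3.13 requires every post-entry laboratory value on the case report form, whatever its grade.

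**The concern.** A participant whose platelet count falls to Grade 3 without symptoms has an AE under 7.1. Under 7.6 that participant has one only if one of the four conditions is met. Blood-count toxicity is the linezolid effect the plan powers for, and it is often found by a scheduled count and not by a complaint. The endpoint could therefore miss part of what it is meant to measure.

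Two analysts could each follow the documents and count different events. One count would depend on symptoms and investigator judgment in an open-label trial, where section 4.0 promises only an effort to blind the staff who assess AEs. The other would depend on the blood count alone. Any under-recording would lower the estimated frequency of toxicity, reduce power for linezolid versus no linezolid, and weaken the exposure-response analysis.

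**Working it through.** **The text**

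| Question | 7.1 and 7.2 | 7.6 |
|---|---|---|
| Is a silent abnormal laboratory value an AE? | Yes | Only under one of four conditions |
| Does Grade 3 or higher settle it? | Yes: 7.2 has all such AEs recorded | No: no condition mentions grade |
| Is a repeat blood count enough? | Not needed | Expressly not |
| Does judgment enter? | No | Yes, through the fourth condition |

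The direct conflict is between 7.1 and 7.6. The conflict with 7.2 follows only if 7.1 defines an AE; if 7.6 does, a silent cytopenia is not an AE and 7.2 is never reached. Reading the 7.6 rule as one about expedited reporting does not remove the conflict. The section concerns recording, speaks of the AE endpoint, and states when a result is an AE at all. Reporting of serious events is handled separately in 7.7.

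**Which outcomes are exposed**

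- *2.4 Grade 3 or higher AE endpoints:* directly, because they are worded as AEs.
- *10.2 myelosuppression:* only if AE forms supply the data. Sections 6.1 and 6.3.13 put every scheduled count (weeks 1, 2 and 4) on the case report form in all arms.
- *10.2 discontinuation or dose reduction:* the stop itself is documented. Section 9.1 has drug discontinuation or dose modification entered on the follow-up form, 8.0 requires notification within 24 hours of toxicities that change study treatment, and 6.3.3 records TB drug modifications. The open point is only whether a stop prompted by a laboratory value counts as one attributed to an AE.

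**The plan's power figure**

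Inputs from 10.1: 40% versus 10% myelosuppression, 30 per arm, significance level 0.05 (two-sided assumed), at least 80% power.

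- Pooled normal formula: [0.30 − 1.96 × √(2 × 0.25 × 0.75 / 30)] / √(0.40 × 0.60 / 30 + 0.10 × 0.90 / 30) = (0.30 − 0.219) / 0.105 = 0.77, so power 78.0%.
- Unpooled: 0.30 / 0.105 − 1.96 = 0.90, so power 81.6%.
- Exact enumeration of the uncorrected chi-square test: 79.6%.

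The stated figure is reproduced to within about 2 points.

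**Illustration for myelosuppression if AE forms were the source**

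The test in 10.2 is Cochran-Mantel-Haenszel across rifampicin dose. Two 1:1 randomizations of 60 give 15 per cell. In stratum k, let a be the linezolid events and m the total events among 30. The statistic is [Σ(a − m/2)]² / Σ[m(30 − m)/116], where 116 = 4 × 29, compared with 3.84. Power comes from full enumeration of the binomial outcomes, with both true rates multiplied by an assumed capture share s.

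| s (assumed) | Expected linezolid events counted (30 × 0.40 × s) | Expected no-linezolid events counted (30 × 0.10 × s) | Power |
|---|---|---|---|
| 100% | 12 | 3 | 79.9% |
| 95% | 11.4 | 2.85 | 77.0% |
| 90% | 10.8 | 2.7 | 73.9% |
| 75% | 9 | 2.25 | 63.9% |

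Section 10.1 also mentions 20 participants on linezolid with high-dose rifampicin. Strata of 10 and 20 per arm change these results by about 0.1 point. No continuity correction is applied, since 10.2 specifies none.

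**2.4 endpoints**

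No figure can be derived. The documents give neither the overall Grade 3 or higher AE rate nor the share of silent cytopenias that 7.6 would leave out.

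**The case against.** The best defense is that the practical loss may be small. Section 8.1.2 calls counts beyond its limits a hematological toxicity and has linezolid stopped. An investigator who stops study drug for a blood count could hardly call that count insignificant, so the fourth condition would normally bring it in. The filter in 7.6 is also a sensible way to limit AE paperwork in a critically ill population. A participant with any other Grade 3 or higher event still counts in the 2.4 proportion. Section 7.4 expects death from the disease in about 40% of participants, and section 1.0 places most deaths in the first month, so a missed cytopenia changes that endpoint less than it would a cytopenia-only outcome.

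Most of this stands, and it limits the size of the point. It does not remove the contradiction: the fourth condition is discretionary, and grade alone never makes a result an AE.

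A reader might infer three stronger conclusions that the documents do not support:

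- *That the trial's power is really 74% or 64%.* The capture shares are assumptions, 10.1 does not say that its 40% and 10% are Grade 3 or higher rates, and deriving an outcome defined by blood counts from blood counts is the natural reading.
- *That linezolid stops go unrecorded.* Sections 9.1, 8.0 and 6.3.3 document them.
- *That recording differs by arm.* This is possible in an open-label trial, but nothing in the documents shows it.

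**Conclusion.** The point holds as a contradiction between 7.1 and 7.6, with a conflict with 7.2 wherever 7.1's definition governs. It can omit silent Grade 3 or higher cytopenias, the main linezolid toxicity of interest, from the 2.4 proportion and exposure-response endpoints. The number is unknown.

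For myelosuppression in 10.2 the effect is conditional on AE forms being the source. In that case, capture of 95%, 90% or 75% would cost about 3, 6 or 16 points of power. This assumes equal capture in both arms, true Grade 3 or higher rates of 40% and 10%, and a two-sided uncorrected test. For the discontinuation outcome only the meaning of attribution to an AE is open.

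The primary pharmacokinetic endpoints are untouched and every blood count is kept, so the matter can be settled in wording before analysis. It should be settled, because otherwise the event definition could be chosen after the data are seen.

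**What to change.** 1. In 10.2, derive Grade 3 or higher myelosuppression in all four arms from every hematology value recorded after entry through week 4, scheduled or not. Grade by the DAIDS table and require a grade worse than baseline, in line with 7.1. Baseline is the entry count, or the screening count where Table 5 allows entry tests to be deferred. Symptoms and AE reporting play no part.
2. Reconcile 7.6 with 7.1 and 7.2 by stating that these laboratory-derived hematologic events also count in the 2.4 Grade 3 or higher AE and exposure-response endpoints. The reporting filter in 7.6 can otherwise stay. Whether silent chemistry and liver values also count is for the sponsor to choose and state.
3. In 10.2, state that a linezolid stop or dose reduction prompted by a recorded laboratory value counts in the discontinuation outcome.

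The cost is wording in 7.6 and 10.2, with a cross-reference from 2.4. No visits, samples or AE forms are added, and no clinical management rule changes. The downside is that some clinically silent values will count as events.
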